3.4.4 Prohibited or Restricted Therapies

The following therapies are prohibited while the subject is on study:

- Any investigational agent or investigational medical device;
- Any drug or herbal product used specifically for the treatment of ACC ;
- Oral anticoagulation with coumarin agents (e.g., warfarin), direct thrombin inhibitors (e.g., dabigatran), direct factor Xa inhibitor betrixaban, platelet inhibitors (e.g., clopidogrel), and chronic use of aspirin above low dose levels for cardio-protection per local applicable guidelines), until 4 weeks after cabozantinib has been permanently discontinued.
- Any other systemic anticancer treatment (e.g., chemotherapy, immunotherapy, radionuclides) and local anticancer treatment such as surgery, ablation, or embolization.

The following therapies should be avoided if possible, while the subject is on study:

- Palliative external radiation to bone metastasis for bone pain should not be routinely performed while on study but can be considered as a treatment for non-target lesions at the investigator's discretion.
- Erythropoietic stimulating agents (e.g., epoetin alfa and darbepoetin alfa) should not be used based on a report of increased risk of tumor recurrence and/or progression associated with erythropoietin;
- Chronic co-administration of cabozantinib with strong inducers of the CYP3A4 family (e.g., phenytoin, carbamazepine, rifampin, rifabutin, rifapentine, phenobarbital, and St. John's Wort) may significantly decrease cabozantinib concentrations and should be avoided if possible. Selection

Proprietary Information of MD Anderson

of alternate concomitant medications with no or minimal CYP3A4 enzyme induction potential is recommended;

- Caution must be used when discontinuing treatment with a strong CYP3A4 inducer in a subject who has been concurrently receiving a stable dose of cabozantinib, because this could significantly increase the exposure to cabozantinib;
- Co-administration of cabozantinib with strong inhibitors of the CYP3A4 family (e.g., itraconazole, clarithromycin, indinavir, nefazodone, nelfinavir, and ritonavir) may increase cabozantinib concentrations and is not permitted. Grapefruit and Seville oranges may also increase plasma concentrations of cabozantinib and should be avoided. Ketoconazole use will be permitted to treat Cushing syndrome if clinically unavoidable. Cabozantinib dose needs to be reduced by 20 mg when using ketoconazole. Resuming prior dose level is permitted 2-3 days after discontinuing ketoconazole.

Additional information on potential drug interactions with cabozantinib is provided in Section 3.4.5.

3.4.5 Potential Drug Interactions

Cytochrome P450 (CYP): Data from a clinical drug interaction study (Study XL184-008) show that clinically relevant steady-state concentrations of cabozantinib appear to have no marked effect on the area under the plasma drug concentration time curve (AUC) of co-administered rosiglitazone, a CYP2C8 substrate. Therefore, cabozantinib is not anticipated to markedly inhibit CYP2C8 in the clinic, and by inference, is not anticipated to markedly inhibit other CYP450 isozymes that have lower [I]/Ki values compared with CYP2C8 (i.e., CYP2C9, CYP2C19, CYP2D6, CYP1A2, and CYP3A4). In vitro data indicate that cabozantinib is unlikely to induce cytochrome P450 enzymes, except for possible induction of CYP1A1 at high cabozantinib concentrations (30 μ M).

Cabozantinib is a CYP3A4 substrate and a weak substrate for CYP2C9 (but not a CYP2D6, CYP2C8, CYP2C19, CYP2B6, or CYP1A2 substrate), based on data from in vitro studies. Results from a clinical pharmacology study, XL184-006, showed that concurrent administration of cabozantinib with the strong CYP3A4 inducer, rifampin, resulted in an approximately 77% reduction in cabozantinib exposure (AUC values) after a single dose of cabozantinib in healthy volunteers. Chronic co-administration of cabozantinib with strong inducers of the CYP3A4 family (eg, phenytoin, carbamazepine, rifampin, rifabutin, rifapentine, phenobarbital, and St. John's Wort) may significantly decrease cabozantinib concentrations. The chronic use of strong CYP3A4 inducers should be avoided. Other drugs that induce CYP3A4 should be used with caution because these drugs have the potential to decrease exposure (AUC) to cabozantinib. Selection of alternate concomitant medications with no or minimal CYP3A4 enzyme induction potential is recommended.

Results from a clinical pharmacology study, XL184-007, showed that concurrent administration of cabozantinib with the strong CYP3A4 inhibitor, ketoconazole, resulted in a 38% increase in the cabozantinib exposure (AUC values) after a single dose of cabozantinib in healthy volunteers. Co-administration of cabozantinib with strong inhibitors of the CYP3A4 family (eg, ketoconazole, itraconazole, clarithromycin, indinavir, nefazodone, nelfinavir, and ritonavir) may increase cabozantinib concentrations. Grapefruit and Seville oranges may also increase plasma concentrations of cabozantinib and should be avoided. Strong CYP3A4 inhibitors should be avoided and other drugs that inhibit

Proprietary Information of MD Anderson

CYP3A4 should be used with caution because these drugs have the potential to increase exposure (AUC) to cabozantinib. Selection of alternate concomitant medications with no or minimal CYP3A4 enzyme inhibition potential is recommended.

In addition, cimetidine should be avoided because of its potential to interfere with CYP3A4 mediated metabolism of cabozantinib.

Please refer to the drug interaction tables at the following websites for lists of substrates, inducers, and inhibitors of selected CYP450 isozyme pathways:

<Http://medicine.iupui.edu/clinpharm/ddis/table.aspx>

<http://www.fda.gov/Drugs/DevelopmentApprovalProcess/DevelopmentResources/DrugInteractionsLabeling/ucm080499.htm>

Protein Binding: Cabozantinib is highly bound ($\geq 99.7\%$) to human plasma proteins. Therefore, highly protein bound drugs should be used with caution with cabozantinib because there is a potential displacement interaction that could increase free concentrations of cabozantinib and/or a co-administered highly protein-bound drug (and a corresponding increase in pharmacologic effect).

Other Interactions:

Food may increase exposure levels of cabozantinib by 57%, fasting recommendations should be followed. Subjects should fast (with the exception of water) for at least 2 hours after eating the evening meal before taking their dose of cabozantinib. After the 2-hour fast and before going to bed, subjects are to take cabozantinib with a full glass of water (minimum of 8 oz or 240 mL) with no more food intake for one hour post-dose.

In vitro data suggest that cabozantinib is unlikely to be a substrate for P-glycoprotein, but it does appear to have the potential to inhibit the P-glycoprotein transport activity. Therefore, cabozantinib may have the potential to increase plasma concentrations of co-administered substrates of P-glycoprotein.

Cabozantinib was shown to be a substrate of drug transporter MRP2 in an in vitro assay. Administration of MRP2 inhibitors to subjects may result in increases in cabozantinib plasma concentrations.

Additional details regarding potential drug interactions with cabozantinib can be found in the latest version of the investigator brochure.

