3.2 Dose, Schedule and Route

Subjects will receive cabozantinib orally at a (starting) dose of 60 mg once daily, on a continuous basis.

Proprietary Information of MD Anderson

Cabozantinib must be taken on an empty stomach. Subjects must be instructed not to eat for at least 2 hours before and at least 1 hour after taking cabozantinib. Subjects should be instructed to take their cabozantinib dose at approximately the same time every day. If a subject misses a dose, the dose may be taken later only if it is within 12 hours of when the missed dose should have been taken. The missed dose should not be made up if it is within 12 hours of the next scheduled dose.

Cabozantinib tablets should be swallowed whole with at least 8 ounces of water. The tablets should not be crushed. Grapefruit, grapefruit juice, Seville oranges and their products should be avoided by subjects taking cabozantinib.

In all subjects, dose reductions and delays to manage toxicity are allowed under the guidelines in Section 3.3 below.

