³All sites of known disease must be assessed with CT or MRI. In patients with IV contrast allergy or borderline renal function, CT without IV contrast or 18 FDG PET CT may be used as clinically indicated.

⁴ No additional measurements of adrenal hormones (ACTH, cortisol, aldosterone, plasma renin activity, DHEA-sulfate, testosterone in women, estradiol in men and postmenopausal women) are needed in patients with normal profile at baseline (Non-functioning ACC).

⁵ No need for mitotane measurement in patients who have been off mitotane for > 6 months or never received mitotane.

⁶Full pharmacokinetic assessment on day 1 and day 29(+/- 5 days) then one trough level every 12 weeks (+/- 6 weeks); On day 1 and 29 (+/- 5 days): PK blood samples (10 mL) are to be collected within 15 minutes prior to dosing of cabozantinib and at the following time points following ingestion of the dose: 1 hour (\pm 15 minutes), 2 hours (\pm 15 minutes), 4 hours (\pm 15 minutes), and 8 hours (\pm 15 minutes) post-dose.

⁷ Optional imaging guided biopsy from an accessible tumor site to be done at baseline, 29 days (+/- 5 days), and at time of progression.

⁸ If QTcF interval within normal range at baseline and subsequent ECGs at weeks 3 and 5, then no need for routine ECG monitoring. ECGs may be ordered as needed if there is other clinical indication.

⁹ Within 48 hours prior to day 1

¹⁰ Consider 24-hour urine collection for protein if UPCR>1mg/mg

¹¹ A 50 cc blood sample to be collected for immunologic testing at screening, at week 9 day 1(+/- 5 days), and at progression (+ 5 days). A 10 cc to be collected for pharmacogenetic screening at screening only.

¹² If abnormal at baseline or clinically indicated

If the subject is unable to have a study assessment taken within the defined time window due to an event outside of his or her control (e.g., clinic closure, personal emergency, inclement weather, vacation), the assessment should be performed as close as possible to the required schedule.

Regular tumor assessments should be performed in accordance to the guidelines in Section 5.5 to determine if PD is present.

The Treatment Period ends when a subject receives his or her last dose of study treatment; the subject then enters the Post-Treatment Period.

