8 OTHER ANALYSES

Blood samples for pharmacokinetics and pharmacogenetics studies will be collected during study course. However, analysis is planned to occur after data is completely collected, except in the subset of subjects who previously used mitotane within 6 months of study participation. This subset's PK samples will be analyzed shortly after collection to guide cabozantinib dosing.

PK profiles will be obtained on first dose (Day 1) and at steady-state (Day 29 +/- 5 days) after starting study drug. In addition, 1 blood sample will be collected every 12 weeks (+/- 6 weeks) to measure cabozantinib trough levels. If feasible, blood samples will be collected at the time of disease progression or significant toxicity (CTACE grade 3 or more). For determining PK profiles, PK blood samples (10 mL) are to be collected within 15 minutes prior to dosing of cabozantinib and at the following time points following ingestion of the dose: 1 hour (\pm 15 minutes), 2 hours (\pm 15 minutes), 4 hours (\pm 15 minutes), and 8 hours (\pm 15 minutes) post-dose. Blood samples (~10 ml) for the determination of steady-state trough concentrations of cabozantinib will be collected immediately prior to the patient's first dose of the day. The time and date of the patient's prior dose, and time and date of blood sampling will be clearly documented in the patient's medical chart. At each collection point, whole blood (10 mL) will be collected into pre-chilled lavender-top (or similar) collection tubes and immediately placed on wet ice. Within 30 minutes of collection, chilled tubes will be centrifuged at 1,500 x g for 15 min at 4°C. Plasma (supernatant) will be immediately transferred to pre-labelled cryovials and stored at -80°C until assayed. Plasma concentrations of cabozantinib will be measured by a validated liquid chromatography-mass spectrometry (LC-MS/MS) assay in a validated laboratory (World Wide Clinical Trials [WWCT], Austin, Texas). All PK samples will be split into two ~2.5 mL plasma samples, with only one (primary) sample being shipped to WWCT for analysis and the other (backup) retained in pre-labelled cryovials and stored at -80°C. All samples that will be analyzed after study completion will be also stored at -80°C until assayed.

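### Bedtime dosing in Section 3.4.5 and the 0 to 8 hour PK schedule cannot both be followed at a daytime visit, so the Day 29 AUC used for dosing may be biased up or down

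*Combined protocol and SAP*

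**What the plan says.** - **Time of dosing.** Section 3.4.5, in its paragraph on food, says: "After the 2-hour fast and before going to bed, subjects are to take cabozantinib with a full glass of water". Section 3.2 gives no hour: "Subjects should be instructed to take their cabozantinib dose at approximately the same time every day".
- **Dosing interval.** Section 3.2: "Subjects will receive cabozantinib orally at a (starting) dose of 60 mg once daily, on a continuous basis". On missed doses it adds: "The missed dose should not be made up if it is within 12 hours of the next scheduled dose".
- **PK profiles.** Section 8: "PK profiles will be obtained on first dose (Day 1) and at steady-state (Day 29 +/- 5 days) after starting study drug". On both days, Table 5-1 footnote 6 states: "PK blood samples (10 mL) are to be collected within 15 minutes prior to dosing of cabozantinib". Further samples follow at 1, 2, 4 and 8 hours after ingestion.
- **Troughs.** One sample is due every 12 weeks (+/- 6 weeks). Section 8 says that trough samples "will be collected immediately prior to the patient's first dose of the day".
- **Use of the profiles.** Sections 1.3.1 and 3.3 permit a dose increase in subjects who used mitotane within 6 months if plasma AUC is below 50% of the expected AUC. The PK for this comes from Day 1 and Day 29, and Section 3.3 adds a condition on adverse event grade. Section 8 has these subjects' samples analysed shortly after collection. For an estimated 12 of 18 subjects, samples are analysed only after enrolment is complete.
- **Recording.** Section 8 requires the times of the prior dose and of blood sampling to be documented in the chart.

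**The concern.** After a bedtime dose, the samples at 1 to 8 hours fall overnight. The schedule reads like a daytime procedure, with five timed draws, tubes placed on ice at once and centrifugation within 30 minutes. No section provides for overnight sampling or says how the dose before a PK visit is handled.

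A patient who doses at bedtime and attends a daytime Day 29 visit must therefore depart from the usual interval. One way is to take a dose at the visit some 10 to 12 hours after the last one. The other is to omit the evening dose and arrive some 34 to 36 hours after it. Either breaks the same-time instruction, and the two push the measured exposure in opposite directions.

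In about 18 - 12 = 6 patients, the Day 29 profile feeds a dosing decision made soon after collection. The recorded dose times are not tied to any adjustment of the AUC or to any check on the profile. In the others, mistimed samples would add noise to exploratory PK analyses in a trial of at most 18 patients.

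**Working it through.** **Inputs from the protocol.** CL/F 4.4 L/h, V/F 349 L, effective half-life about 55 h, Tmax 2 to 5 h and accumulation 4- to 5-fold (Section 1.2.3.3); 60 mg every 24 h (Section 3.2); samples at 0, 1, 2, 4 and 8 h (Section 8).

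**Assumptions, not in the documents.**
- One compartment with first-order absorption, ka 0.6 to 2.0/h. Model Tmax is 6.6 to 2.5 h; ka of 1 to 2 gives 4.4 to 2.5 h, inside the stated range.
- Daytime PK visits, with the gaps given above.
- CL/F doubled to 8.8 L/h for a patient whose true AUC (dose divided by CL/F) is half the population value.

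**Step 1: reproduce the stated half-life.** k = 4.4/349 = 0.01261 per h, and ln 2/k = 54.98 h, against 55 h stated. Accumulation is 1/(1 - exp(-24k)) = 3.83, just below the stated 4- to 5-fold.

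**Step 2: pre-dose level.** Once absorption is complete, the level g hours after the last dose, relative to the 24-hour trough, is exp(k(24 - g)).
- CL/F 4.4: g = 10 gives 1.193; 12 gives 1.163; 34 gives 0.882; 36 gives 0.860.
- CL/F 8.8 (k = 0.02521): 1.423, 1.353, 0.777 and 0.739.

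**Step 3: AUC0-8.** The new dose contributes the same amount whatever the gap. Only the carry-over from earlier doses changes, and over 8 h it is C0 x (1 - exp(-8k))/k. At ka = 1/h:
- CL/F 4.4: C0 = 0.493 mg/L, so carry-over is 0.493 x 7.61 = 3.75 of a total 4.88 mg.h/L, or 77%. A 19.3% rise in the pre-dose level becomes about 15% in AUC0-8.
- CL/F 8.8: C0 = 0.212 mg/L, so carry-over is 0.212 x 7.24 = 1.54 of 2.62, or 59%. A 42.3% rise becomes about 25%.

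Full superposition with linear trapezoids, over the whole ka range:

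| Gap before the Day 29 profile dose | Pre-dose, CL/F 4.4 | AUC0-8, CL/F 4.4 | Pre-dose, CL/F 8.8 | AUC0-8, CL/F 8.8 |
|---|---|---|---|---|
| 24 h | 0 | 0 | 0 | 0 |
| 10 to 12 h | +16% to +19% | +12% to +15% | +35% to +42% | +20% to +26% |
| 34 to 36 h | -12% to -14% | -9% to -11% | -22% to -26% | -13% to -16% |

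**Step 4: the 50% rule, as illustration only.** Suppose the expected AUC means AUC0-8 at CL/F 4.4 with a 24-hour gap. A patient whose true AUC is 50% of expected then reads 53% to 54% with correct timing, 64% to 67% after a 10 to 12 hour gap, and 44% to 47% after a 34 to 36 hour gap. The true AUC that reads as exactly 50% is about 46% to 47% with correct timing and 33% to 36% after a 10 to 12 hour gap. Part of the distance from 50% is therefore not a timing effect: it comes from using an 8-hour window. The documents define neither the expected AUC nor its interval, so no exact shift can be derived.

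**Step 5: what is not affected.** On Day 1 there is no earlier dose and no carry-over, so no timing bias. A trough drawn just before the usual once-daily dose is a true 24-hour trough. Only a trough drawn at another point in the interval is off; 10 to 12 hours after a bedtime dose it would carry the pre-dose errors in the table.

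**The case against.** The strongest reply is that Section 3.2 is the governing dosing section. It lets a patient dose at one daytime hour throughout, and then there is no timing bias at all. The bedtime sentence sits in a paragraph on food effects and may be meant only to explain fasting. That is a fair account of what may happen in practice, but the sentence is worded as an instruction, and nothing gives Section 3.2 precedence.

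A reader might go further and infer that the Day 29 AUC and the troughs are biased upward, in all 18 patients. The documents do not support that:
- An upward error needs the bedtime dose to be kept and another dose to follow 10 to 12 hours later. No section asks for this, and it is a spacing that the missed-dose rule avoids. Omitting the evening dose gives a downward error.
- Neither sampling section says that the dose is observed or taken in clinic. The daytime visit is an inference.
- Troughs are mistimed only if drawn away from the usual dose, contrary to Section 8. The reference there to the day's first dose is odd wording for once-daily treatment, but does not itself cause an error.
- The dose rule draws on Day 1 as well as Day 29, and Day 1 cannot carry this error.

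The recorded dose times do allow correction in the roughly 12 patients analysed after enrolment. They protect less well in the other 6 or so, whose results are used soon after collection, because no correction is planned.

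**Conclusion.** The conflict stands, and it is worth correcting because a dosing decision depends on one of the affected measurements. On the assumption of daytime PK visits, the bedtime instruction, the same-time instruction and the sampling schedule cannot all be followed, and the protocol does not say which gives way. The Day 29 AUC0-8 may be about 12% to 15% too high or 9% to 11% too low at the protocol's clearance. It may be 20% to 26% too high or 13% to 16% too low in a patient with doubled clearance, who is the kind of patient the 50% rule is meant to find. A patient near the threshold could be misclassified in either direction.

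These sizes rest on a one-compartment model, an assumed ka, assumed gaps, and CL/F and V/F estimated at 140 mg daily in subjects with solid tumours including MTC. Section 1.2.3.3 notes higher clearance in MTC than in RCC; if clearance here is lower and V/F similar, the errors shrink. The consequence is confined to PK-guided dosing in about 6 patients and to the exploratory PK objectives. PFS4 is not directly affected.

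**What to change.** 1. The sponsor should reconcile Sections 3.2, 3.4.5, 8 and Table 5-1, so that the dosing-time instruction and the PK sampling schedule can both be followed and the text says how the dose before a PK visit is handled. The choice of dosing time is the sponsor's; this review takes no position on it.
2. Reword the trough instruction in Section 8 to fit once-daily dosing.
3. State in Section 8 that AUC and troughs are calculated and interpreted by actual time since the previous dose, using the times already recorded, and that profiles not taken at the regular dosing interval are flagged.

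The cost is minor wording and some analysis work, with no added visits or samples. A few profiles may end up flagged.

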3.5 Compliance

Drug accountability and subject compliance will be assessed with drug dispensing and return records.

3.6 Study Drug Accountability

The investigator will maintain accurate records of receipt of all cabozantinib, including dates of receipt. In addition, accurate records will be kept regarding when and how much study treatment is dispensed and used by each subject in the study. Reasons for deviation from the expected dispensing regimen must also be recorded. At completion of the study, to satisfy regulatory requirements regarding drug accountability, all unused cabozantinib will be reconciled and destroyed in accordance with applicable state and federal regulations and in accordance to MD Anderson institutional policies and procedures for drug destruction.

Proprietary Information of MD Anderson

4 STUDY POPULATION

4.1 Inclusion Criteria

A subject must fully meet all of the following criteria to be eligible for the study:

1. The subject is \geq 18 years old on the day of consent
2. Histological confirmation of ACC based on either: i). Weiss Score of \geq 3 in patients who had earlier surgical resection (*Lin-Weiss-Bisceglia system* will be used for oncocytic ACC) OR ii). biopsy results compatible with ACC in the context of clinical setting highly suggestive of ACC (adrenal mass $>$ 4 cm invading surrounding organs or associated with distant metastases).
3. Locally advanced or metastatic disease not amenable to surgery with curative intent with measurable disease per RECIST 1.1 (9) as determined by the investigator based on an assessment of all known disease sites by computerized tomography (CT) scan or magnetic resonance imaging (MRI) of chest/abdomen/pelvis within 28 days before the first dose of cabozantinib. In patients with IV contrast allergy or borderline renal function, CT without IV contrast or 18 FDG PET CT may be used as clinically indicated
4. Eastern Cooperative Oncology Group (ECOG) performance status of 0-2
5. Recovery to baseline or \leq Grade 1 CTCAE v.4.0 from toxicities related to any prior treatments, unless AE(s) are clinically non-significant and/or stable on supportive therapy
6. Life expectancy of at least 3 months
7. Organ and marrow function and laboratory values as follows within 28 days prior to the first dose of cabozantinib:
 - a. Absolute neutrophil count (ANC) \geq 1500/mm³ without colony stimulating factor support
 - b. Platelets \geq 100,000/mm³
 - c. Hemoglobin \geq 9 g/dL
 - d. Bilirubin \leq 1.5 \times the upper limit of normal (ULN). For subjects with known Gilbert's disease, bilirubin \leq 3.0 mg/dL
 - e. Serum albumin \geq 2.8 g/dL
 - f. Serum creatinine \leq 1.5 \times ULN or creatinine clearance (CrCl) \geq 50 mL/min. For creatinine clearance estimation, the Cockcroft and Gault equation should be used:
Male: CrCl (mL/min) = $(140 - \text{age}) \times \text{wt (kg)} / (\text{serum creatinine} \times 72)$. Female: Multiply above result by 0.85
 - g. Alanine aminotransferase (ALT) and aspartate aminotransferase (AST) \leq 3.0 \times ULN
 - h. No radiologic or clinical evidence of pancreatitis
 - i. Urine protein/creatinine ratio (UPCR) \leq 1
 - j. Serum phosphorus \geq 2.5mg/dL, cCalcium \geq 8mg/dL, magnesium \geq 1.2mg/dL, and potassium \geq 3.0 meq/L (CTCAE V4.03 grade 1 cut off levels).
8. Capable of understanding and complying with the protocol requirements and has signed the informed consent document.
9. Sexually active patients (men and women) must agree to use medically accepted barrier methods of contraception (e.g. male or female condom) during the course of the study and for 4 months after the last dose of study drug(s), even if oral contraceptives are also used. All sexually active

Proprietary Information of MD Anderson

subjects of reproductive potential must agree to use both a barrier method and a second method of birth control during the course of the study and for 4 months after the last dose of study drug(s).

- a. Women of childbearing potential must have a negative pregnancy test at screening. Women of childbearing potential include women who have experienced menarche and who have not undergone successful surgical sterilization (hysterectomy, bilateral tubal ligation, or bilateral oophorectomy) or are not postmenopausal. Postmenopause is defined as amenorrhea \geq 12 consecutive months. Note: women who have been amenorrheic for 12 or more months are still considered to be of childbearing potential if the amenorrhea is possibly due to prior chemotherapy, anti-estrogens, ovarian suppression or any other reversible reason.

